3.2. Exclusion Criteria

- 3.2.1. Patient is currently smoking or using tobacco or nicotine products (i.e. patch, gum, or nasal spray) or has used such products in the past 12 months.
- 3.2.2. Patient has a history of delayed wound healing, Vitamin C deficiency, diabetes (Type I or Type II), BMI<18.5 or >40 kg/m, or any other uncontrolled comorbidity.
- 3.2.3. Patient is currently receiving radiation or chemotherapy or received radiation to the breast wall.
- 3.2.4. Patient has a history of prior NAC reconstruction
- 3.2.5. Patient has had NAC tattooing.
- 3.2.6. Therapy restrictions: none
- 3.2.7. Investigational Agent restrictions: none
- 3.2.8. Patient has a history of allergic reaction to any decellularized biologic matrix product.
- 3.2.9. No patient will be excluded from the study due to history of HIV or cancer.

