2.2. Study Device

The BioAesthetics NACgraft™ is a decellularized NAC derived from deceased human donors. Proprietary washing/rinsing steps provide a removal of immunologic elements (including cells and nucleic acids). The NACgraft™ is then packaged in a tube containing sterile PBS for individual attachment to a de-epithelialized portion of the human breast after breast reconstruction and is protected with dressings until re-vascularization, re-epithelialization and dermal/neural elements repopulate the device, leaving a living human NAC substitute. By preserving the ECM of the native human NAC, including its non-immunogenic signaling molecules and structural format, the BioAesthetics NACgraft™ serves as a scaffold that allows vascular, neural, dermal and epithelial infiltration until the time of complete healing. The BioAesthetics NACgraft™ has been studied extensively in *in vitro* and in preclinical models including mice and non-human primates to demonstrate their safety and therapeutic potential, as detailed in Section 2.5.^{21,22}

BioAesthetics' NACgraft™ fits within the Food and Drug Administration (FDA)'s HCT/P (Human Cells, Tissues, and Cellular and Tissue-Based Products (21 CFR Part 1271)) regulatory pathway (see Appendix A1 of Investigator's Brochure). To advance to clinical use, the product is manufactured in accordance with Current Good Tissue Practices (CGTP) and must submit a registration with the FDA 90 days prior to marketing. The NACgraft™ will be registered with the FDA prior to study initiation. Therefore, no Investigational Device Exemption (IDE) is required for this feasibility study.

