2.5. Correlative Studies Background

The BioAesthetics NACgraft™ has been studied extensively in *in vitro* and in preclinical models to demonstrate their safety and therapeutic potential, as detailed below.^{21,22}

In a recent study,²¹ NAC tissue was harvested from rhesus macaques according to institutional guidelines and decellularized through a modified protocol.^{23,24} Briefly, NAC grafts are incubated with a series of agents alternating with water including Triton X-100, sodium deoxycholate, sodium chloride, antibiotic/antimycotic agents, and DNase I, then stored in antibiotic/antimycotic solution until use. This process removes cellular components while preserving the extracellular matrix (ECM) structure. Decellularized NACs were subjected to histological and quantitative analyses, including culture with bone marrow-derived mesenchymal stem cells (BMSCs) *in vitro*. They were found to be completely devoid of cells while retaining ECM integrity and a high degree of bioactivity. Specifically, collagen and glycosaminoglycan content were not significantly altered by decellularization, whereas elastin content was significantly decreased. The graft promoted BMSC proliferation and viability *in vitro*.

In a follow up study, nonhuman primate (NHP)-derived NAC tissue was decellularized and their ECM components analyzed by both proteomic and histological analyses.²² Decellularized NHP NAC grafts again showed the removal of intact cells and a greatly diminished intracellular protein profile, as compared with intact NHP NAC tissue. Decellularized NAC grafts were then tested in a murine model. N=15 mice received subcutaneous implantation of a decellularized-NHP-

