4.2. Criteria for Removal from Study

Reasons for patient withdrawal from the study include the following:

- Patient withdraws consent.
- Patient has disease progression (e.g., breast cancer recurrence on the side(s) of NAC reconstruction), requiring additional treatment such as surgery or chemotherapy.
- Unacceptable adverse events, such as infection, hematoma, or allergic reaction requiring removal of the NACgraft.
- The patient fails to comply with the study guidelines or postoperative care instructions (such as non-adherence with tobacco)
- Any other medical condition which would place the patient at unnecessary risk if they were to continue in the study, determined on a case-by-case basis.

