7. ADVERSE EVENTS AND REPORTING PROCEDURES

7.1. Potential Adverse Events

The potential risks have been identified below. The existing standard of care would be applied to any adverse event. More detailed risk mitigation strategies are described in section 4.3 – Alternatives.

Loss of Privacy and Confidentiality: Potential loss of patient privacy and confidential information is possible.

Medical Risks: The potential risks will be summarized in the consent form and will be reviewed with the patient by the surgeon or study coordinator (as designated in the final protocol). Patients will additionally be able to access a member of the study team with any questions pertaining to risks for this study.

Since a surgical procedure is required for the placement of the BioAesthetics NACgraft™, there are several expected adverse events that are related to the surgery itself. These are similar to the risks with any nipple reconstruction procedure and they include:

- Swelling/edema
- Infection
- Wound contracture
- Pain
- Bleeding
- Lack of or abnormal sensation
- Unanticipated cosmetic result
- Asymmetry
- Scarring
- Need for revisionary procedures

Adverse events that may result from the use of NACgraft™ itself include, but are not limited to the following:

- Lack of device integration
- Lack of device epithelialization
- Device slough
- Abnormal coloration with healing
- Allergic reaction to remaining trace amounts of processing reagents listed in the Cautions section.
- Graft rejection
- Transmission of known pathogens including Hepatitis B or C, HIV I/II, syphilis or other bacteria.
- Transmission or causation of diseases of unknown etiology and characteristics.

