10.2.2. Measurement Definition

Safety of the device will be measured by any observed complications that occur following treatment. Primary safety endpoints will include presence/absence of infection, necrosis, allergic reaction, or any complication that can be attributed to the graft procedure. The degree and frequency of these adverse events will be recorded and reported. These endpoints will be reported in the study case report form (CRF) and will be continuously tabulated and reviewed by the study staff.

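### The only allergy exclusion (3.2.8) does not cover the processing reagents that Section 7.1 names as an allergen of the graft, so a woman with a known reagent allergy is eligible as written

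*Combined protocol and SAP*

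**What the plan says.** Protocol Section 3.2, item 3.2.8, excludes a candidate on one allergy ground only: "Patient has a history of allergic reaction to any decellularized biologic matrix product".

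Section 7.1 separates harms of the surgery from harms of the device. In the device list it gives "Allergic reaction to remaining trace amounts of processing reagents listed in the Cautions section". No section of that name appears in the protocol.

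The only reagent names are in Section 2.5, which describes processing of macaque tissue with a series of agents "including Triton X-100, sodium deoxycholate, sodium chloride, antibiotic/antimycotic agents, and DNase I", the tissue being "then stored in antibiotic/antimycotic solution until use". For the clinical product, Section 2.2 mentions proprietary washing steps without naming reagents, and says: "The NACgraft™ is then packaged in a tube containing sterile PBS".

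On outcomes, Section 10.2.2 states "Primary safety endpoints will include presence/absence of infection, necrosis, allergic reaction", with no restriction on the cause of the reaction. Section 4.2 gives as a reason for withdrawal "Unacceptable adverse events, such as infection, hematoma, or allergic reaction requiring removal of the NACgraft".

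**The concern.** Section 4.3 offers the eligibility criteria as the first clinical safeguard. It says that they select women at acceptably low risk and that characteristics raising the risk of injury lead to exclusion. A documented allergy to a substance that 7.1 says may remain in the graft is such a characteristic, yet nothing in the criteria picks it up. The screener also cannot tell from the protocol which allergies would matter, because the reagent list is cited but not given.

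What is at stake is first the safety of the woman concerned: she could be grafted with a product to which the protocol itself anticipates a reaction. A reaction would then count in a primary safety outcome. If it required removal of the graft, it would be a reason for withdrawal under 4.2. If it were serious, the study would miss the Section 12.7 condition of no serious adverse events.

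**Working it through.** The plan gives no figure on this point, so there is none to reproduce. The check is a comparison of sections, followed by a calculation for scale.

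**Does any criterion catch a known reagent allergy?**

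- 3.1 (inclusion): no item on allergy.
- 3.2.8: a past reaction to a matrix product. A reaction to an antibiotic or a detergent met in another setting does not meet it.
- 3.2.2: the general clause on uncontrolled comorbidity does not mention allergy, and a past drug allergy in a well woman would not ordinarily be called one.
- 3.2.6 and 3.2.7: no therapy or investigational-agent restrictions.
- 4.3: the list of excluded risk characteristics (tobacco, wound healing, vitamin C, diabetes, comorbidity, body mass index, radiation or chemotherapy) has no allergy item.
- Appendix A: nine exclusion items, none on allergy. Even 3.2.8 is absent. That omission is a separate defect, because copying 3.2.8 into the checklist would still leave reagents uncovered.
- Section 9: medical history is taken at Screening, so a reagent allergy may well be recorded, but no criterion turns that record into an eligibility decision.

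So the answer is no.

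**What would one event do to the safety summary?** The input is n = 15 patients (Sections 10.2.1 and 12.6.2).

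- Observed proportion with one event: 1/15 = 6.7%.
- Exact (Clopper-Pearson) lower limit for one event: 1 − 0.975^(1/15) = 0.0017, or 0.2%.
- Exact upper limit: the p that solves (1 − p)^15 + 15p(1 − p)^14 = 0.025, which is p = 0.319, or 31.9%.
- With no event, the exact upper limit is 1 − 0.025^(1/15) = 0.218, or 21.8%.
- Sections 12.1 and 12.3 name the Poisson distribution for incidence rates. On that basis one event gives 0.17 to 37.1 per 100 patients, and no event gives an upper limit of 24.6 per 100.

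One reaction moves the point estimate from 0% to 6.7% and the exact upper limit from 21.8% to 31.9%.

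**How likely is it that such a woman is enrolled?** The documents give no prevalence, so p is an assumption. The chance that at least one of 15 women has a known reagent allergy is 1 − (1 − p)^15:

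| Assumed p | Chance of at least one in 15 |
|---|---|
| 1% | 14% |
| 2% | 26% |
| 5% | 54% |
| 10% | 79% |

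These are chances of enrolling an allergic woman, not of a reaction. If a share r of such women react to the residue, the chance of any event is 1 − (1 − pr)^15. With r = 10%, also an assumption, this is 1 − 0.999^15 = 1.5% at p = 1%, and 1 − 0.99^15 = 14% at p = 10%. The documents support no particular value of p or r.

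**The case against.** The strongest reply is that nothing here is contradictory. Section 7.1 is a list of possible harms and 3.2 a list of exclusions, and a protocol need not pair every harm with an exclusion; device slough and abnormal coloration have none. That is true. A known allergy differs in that it can be identified before surgery by asking, and 4.3 says that the criteria do this kind of selection.

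A second reply is that the Investigator's Brochure or the Instructions for Use, both cited in 4.3, may contain the Cautions section and perhaps a contraindication. They may, and the site may hold the information. But Section 3 and Appendix A do not bring it into eligibility.

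A third is that safeguards exist: medical history at Screening, a discussion of risks with the patient, sign-off by the treating physician and a second reviewer, and removal under 4.2 for a condition posing unnecessary risk. These lower the practical risk. None of them makes a reagent allergy an exclusion.

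Some stronger readings that a reader might infer do not stand:

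- *That the gap biases the safety result.* Residual reagent is part of the graft as supplied, and 7.1 lists the reaction among effects of the device. Counting it under 10.2.2 is correct attribution, and 7.2 requires each event to be assessed for relatedness.
- *That reagents are the allergy risk of the graft.* They are the only allergen named, but the device list in 7.1 is expressly open-ended, and 4.1 lists allergic reaction with no cause.
- *That the clinical graft is stored in antibiotic.* Section 2.5 describes macaque tissue; 2.2 puts the clinical graft in sterile PBS.
- *That 3.2.8 excludes almost nobody because few women have had a matrix product.* The documents say nothing on how many have.

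**Conclusion.** The point holds as a patient-safety gap in eligibility. Section 7.1 says that reagent traces in this product may cause an allergic reaction, and under 3.1, 3.2, 4.3 and Appendix A a woman known to be allergic to such a reagent is not excluded.

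The statistical consequence is modest. One reaction in 15 patients would be reported as 6.7% (exact 95% CI 0.2% to 31.9%) in a descriptive, uncontrolled study that claims no definitive conclusions on its primary outcomes. It would matter more if the reaction were serious, because of the condition in 12.7.

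The conclusion rests on the protocol text alone and assumes that no unseen document already makes reagent allergy a binding exclusion. A reader might take the 14% to 79% range as the risk of a reaction. It is not: it depends on assumed prevalences and stops at enrolment. The reagents left in the human graft, the share of candidates allergic to them and the chance that a trace provokes a reaction are all unstated, so the risk of a reaction cannot be estimated from the documents.

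**What to change.** Reconcile 3.2.8 and Appendix A with 7.1:

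1. Replace the pointer to the Cautions section with the list of reagents that can remain in the human graft as supplied, or with an exact reference to the document and section that holds it.
2. Have the allergy item in 3.2.8 cover known hypersensitivity to those reagents, and carry the full item into the Appendix A checklist, which at present has none.
3. Answer the item from the medical history already taken at Screening; no new procedure is needed.
4. If the sponsor holds that no such reagent remains in the human product, correct 7.1 instead and leave 3.2.8 as it is.

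The cost is one eligibility line, one checklist line and a short list or reference. The downside is that an occasional candidate is screened out. The outcome definition in 10.2.2 needs no change.

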3.3. Informed Consent Process

All participants must be provided a consent form describing the study with sufficient information for participants to make an informed decision regarding their participation. Participants must sign the IRB approved informed consent prior to participation in any study specific procedure. The participant must receive a copy of the signed and dated consent document. The original signed copy of the consent document must be retained in the medical record or research file.

3.4. Randomization Procedures

No randomization will occur.

3.5. Study Timeline

Primary Completion:

The study will reach primary completion 24 months from the time the study opens to accrual.

Study Completion:

The study will reach study completion 24 months from the time the study opens to accrual.

4. TREATMENT PLAN

On the day of surgery, NACgrafts™ will be engrafted according to standard reconstructive technique. Using sterile technique, the recipient site on the breast mound will be de-epithelialized sharply and meticulous hemostasis obtained with electrocautery. The NACgraft™ will then be sutured into the wound bed with dissolving suture (e.g., chromic gut). In women undergoing bilateral NAC reconstruction, this process will be repeated for the contralateral breast. A sterile dressing will be applied, and patients will be discharged home according to institutional guidelines; written instructions will be provided for the care of the NACgraft(s)™ and dressings. The dressing will include antimicrobial ointment, followed by a non-adherent, occlusive dressing (e.g. Adaptic, Xeroform) secured in place using a foam dressing cut into a donut (e.g., Allevyn) to prevent compression of the graft.

Patients will be return to the outpatient clinic regularly until the graft(s) are fully healed: on or about postoperative Days 7, 14, 28, and 42. They will return on days 90, 180, and 360 for measurement of long-term endpoints including nipple dimensions, sensitivity, and for satisfaction survey completion.

In the event that the NAC Graft fails, the surgeon will determine if re-grafting is appropriate. The patient will be offered to undergo a second NAC Graft procedure.

4.1. General Concomitant Medication and Supportive Care Guidelines

Patients will continue their regular medications and receive routine postoperative following NAC reconstruction. No additional supportive medications are needed. No use of radioisotopes or radiation machines are required for the study. The procedures performed are similar to normal postoperative care following NAC reconstruction. The risks associated with the intervention are the same risks as with other surgical NAC reconstruction techniques, and include allergic reaction, asymmetry, swelling, graft failure requiring revision/debridement, hematoma, infection requiring debridement and/or antibiotics, scarring, delayed healing, and unsatisfactory aesthetic results.

4.2. Criteria for Removal from Study

Reasons for patient withdrawal from the study include the following:

- Patient withdraws consent.
- Patient has disease progression (e.g., breast cancer recurrence on the side(s) of NAC reconstruction), requiring additional treatment such as surgery or chemotherapy.
- Unacceptable adverse events, such as infection, hematoma, or allergic reaction requiring removal of the NACgraft.
- The patient fails to comply with the study guidelines or postoperative care instructions (such as non-adherence with tobacco)
- Any other medical condition which would place the patient at unnecessary risk if they were to continue in the study, determined on a case-by-case basis.

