10. MEASUREMENTS

10.1. Primary outcome measure: time to complete healing

10.1.1. Relevant Subset

All patients (n=15).

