10.1.2. Measurement Definition

Time to healing for each NACgraft will be as the first weekly visit at which the surgeon deems the graft >99% overall healed. This measurement will be reported as the number of weeks to healing.

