10.1.3. Measurement Methods

Degree of healing will be based on visual assessment by the surgeon with the following metrics on a visual analog scale (VAS): vascularization, overall healing (0-100%). Photographs will be taken, stored and transmitted securely to BOX. Time to complete healing will be defined as the first visit at which the surgeon determine that there is >99% overall healing of the graft.

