12.4. Primary Analysis

Primary outcome measure: To evaluate safety and healing rates following NAC reconstruction using the BioAesthetics NACgraft™.

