12.4.1. Analysis Population

All study participants will be included in the analysis population. Intention-to-treat analysis will be performed and statistics for sub-groups containing no missing data or non-adherence will be included.

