12.4.2. Analysis Plan

Time to complete healing for each NAC will be defined (as described in **Section 10.1**) as the first weekly visit at which the surgeon deems the graft >99% overall healed. This outcome will be characterized in terms of distributional characteristics such as the maximum, mean, median, and variation (as 95% confidence interval) of these data.

Safety outcome data as described in **Section 10.2** that are reported as percentages (ischemia/necrosis, erythema, dehiscence) will be characterized in terms of distributional characteristics such as the maximum, mean, median, and variation (as 95% confidence interval). Measurements reported as categorical variables (infection) will be characterized as a percent.

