12.7. Criteria for future studies

Completion of the study without any serious adverse events, with a >95% healing rate, and with patient survey scores at or above previously published data on patients who have undergone NAC reconstruction, will indicate a positive study result and convince us to continue with a fully powered study. Retention of NAC projection at the level or superior to previously published results will be additional reason to proceed with a larger clinical study.

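### Section 4.2 makes graft removal a reason to withdraw the patient, and no rule gives a graft lost before healing an outcome or says how it counts in the >95% healing criterion

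*Combined protocol and SAP*

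**What the plan says.** - **Withdrawal.** Section 4.2 gives reasons for withdrawing the patient (not the graft). One is "Unacceptable adverse events, such as infection, hematoma, or allergic reaction requiring removal of the NACgraft". The section does not describe any visits, surveys or graft assessments after withdrawal.
- **Re-grafting.** Section 4 says that after a graft fails, the surgeon judges whether re-grafting is suitable and the patient is offered a second procedure. It does not say whether she stays in the study or whether the second graft's healing counts.
- **Primary healing outcome.** Section 10.1.2: "Time to healing for each NACgraft will be as the first weekly visit at which the surgeon deems the graft >99% overall healed". Section 10.1.3 repeats it: "Time to complete healing will be defined as the first visit at which the surgeon determine that there is >99% overall healing of the graft". Section 12.4.2 summarises it by "distributional characteristics such as the maximum, mean, median, and variation (as 95% confidence interval) of these data".
- **Population.** Section 10.1.1 names all 15 patients. Section 12.4.1 includes all participants and adds: "Intention-to-treat analysis will be performed and statistics for sub-groups containing no missing data or non-adherence will be included".
- **Decision rule.** Section 12.7 calls the study positive if it is completed with no serious adverse event, "with a >95% healing rate, and with patient survey scores at or above previously published data". The criterion carries no unit, visit or analysis set.
- **Related provisions.** The synopsis promises each graft's percentage healed across visits. Section 10.2.2 records complications as primary safety endpoints, Section 7.2 follows serious events to resolution or 30 days after treatment, and Section 12.1 commits to assessing data completeness.

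**The concern.** Losing a graft is itself a bad healing outcome. If it also ends the patient's follow-up, data are lost because of the outcome. In a bilateral patient, her other graft may be lost from the data before its result is known.

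The primary summary has the same weakness. A graft lost before >99% healing has no first healed visit, so it cannot enter a mean, median or maximum of healing times unless some rule places it there, and no rule does. The summary then answers how long healing took in the grafts that healed, while the stated aim in Section 12.4 is "To evaluate safety and healing rates following NAC reconstruction using the BioAesthetics NACgraft™".

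At stake are the healing part of the go/no-go in Section 12.7 and the preliminary estimates that Section 12.6.2 intends for sizing the larger study. The study is open-label with one arm, so a counting rule chosen after the data are in would be chosen with the result known.

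**Working it through.** The plan gives no calculation to reproduce: Section 12.6.2 sets 15 patients without a power or precision target.

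**Inputs.** 15 patients, uni- or bilateral (Section 2.4); criterion >95% (Section 12.7). The number of bilateral patients, b, is not given, so I take the range b = 0 to 15, which is n = 15 + b grafts (15 to 30). All losses below occur before >99% healing. For x healed of n, the exact 95% limits are the 0.025 quantile of Beta(x, n − x + 1) and the 0.975 quantile of Beta(x + 1, n − x); the upper limit is 1 when x = n.

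**1. One loss, 15 unilateral patients.**
- All counted: 14/15 = 93.3% (68.1 to 99.8), missed.
- Only grafts with a healing time: 14/14 = 100% (76.8 to 100), met.

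On the second basis the rate is 100% whatever happens, because only healed grafts have a healing time. For comparison, if the true healing probability were 0.90 (an assumption) and losses count, the chance of meeting the criterion with 15 grafts is 0.90^15 = 20.6%.

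**2. Per graft, all grafts counted.**
- One loss passes if (n − 1)/n > 0.95, that is n > 20. At n = 20, 19/20 = 95.0% is not above 95%. At n = 21 (b = 6), 20/21 = 95.2% passes. At n = 30, 29/30 = 96.7% (82.8 to 99.9).
- Two losses pass only if (n − 2)/n > 0.95, that is n > 40, which 15 patients cannot reach: 13/15 = 86.7% up to 28/30 = 93.3%.
- Per patient, one loss is 14/15 = 93.3% and misses at every mix.

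**3. Withdrawal itself.** Take 15 bilateral patients, one withdrawn after removal of one graft while her other graft is not yet healed; all other grafts heal.
- Other graft followed and healed: 29/30 = 96.7%, met.
- Other graft not healed, or counted so because follow-up ended: 28/30 = 93.3% (77.9 to 99.2), missed.
- Both of her grafts left out: 28/28 = 100% (87.7 to 100), met.

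Once follow-up stops, the first two cannot be told apart, and they lie on opposite sides of 95%.

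**4. Time to healing (assumed data).** Suppose 15 grafts, with 2 healed at week 2, 5 at week 4, 5 at week 6, and 3 never.
- Healed only: mean = (2×2 + 5×4 + 5×6)/12 = 54/12 = 4.5 weeks (t-based 95% CI 3.5 to 5.5), median 4, maximum 6.
- All 15 with the unhealed ranked longest: the median is the 8th ordered value, 6 weeks. A mean does not exist without an assigned value.

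The per-graft intervals treat a patient's two grafts as independent.

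**The case against.** The strongest reply is that the plan already decides most of this. Section 12.4.1 includes every participant under intention-to-treat, and for a rate the population is the denominator. On that reading 14/15 is the plan's figure, and 14/14 is at most the additional no-missing-data subgroup. Healing is defined per graft in the synopsis and in Sections 10.1.2, 10.3.2 and 12.4.2, and no section defines a per-patient healing outcome. Per-graft displays would show a lost graft, the event behind a removal is recorded as a safety endpoint, serious events have stated follow-up, and completeness of data will be assessed.

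Much of this stands. A reader might infer that the plan drops failed grafts or leaves the unit wholly open; the documents support neither. What remains is narrower. Intention-to-treat says who is analysed, not what value a graft without a healing time receives. A display of percentages does not supply that value. And 12.7 does not say that it uses the full set, the graft as unit, or any particular visit.

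Two further replies are fair. In a unilateral patient most per-breast survey items make little sense after removal, so what continued visits recover is mainly the items answered once per patient and, in bilateral patients, the other side. Counting every early withdrawal as not healed would also penalise withdrawals that have nothing to do with the graft. The fix allows for both.

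**Conclusion.** The point holds in this form: withdrawal for graft removal comes with no continued data collection, the healing-time summaries describe healed grafts only, and the >95% criterion lacks its set, visit and an explicit unit. A single loss before healing can then meet or miss the healing part of 12.7: 93.3% against 100% with 15 unilateral patients. Per graft with all counted, one loss passes only from 21 grafts up (6 or more bilateral patients).

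Three stronger inferences should be avoided. Section 4.2 lists reasons and does not say that every removal ends participation; patients who heal slowly without removal stay in, and a graft removed after healing keeps its healing time. Sections 4 and 4.2 do not flatly contradict each other, since graft failure and removal for an adverse event overlap without being the same; what is open is the patient's status after the offer of a second graft. Nor does the gap invalidate the study: it is a descriptive pilot without formal tests or a stopping rule, it disclaims definitive conclusions, and all parts of 12.7 must be met together, so a removal classed as a serious adverse event fails it however healing is counted. The documents do not say that every removal would be so classed.

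The counts follow from the documents' 15 patients. The bilateral mix, the healing times and the 0.90 probability are assumptions.

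**What to change.** **(a) Section 4.2.** Separate removal of a graft from the end of data collection. Patients who still consent keep the safety visits already scheduled and the survey items that can still be answered, and a bilateral patient's remaining graft is still assessed.

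**(b) Sections 12.4.2 and 12.7.**
- Use all first grafts as the denominator, and count as not healed any that was removed, re-grafted or failed before reaching >99%.
- Name the visit at which the rate is read. If it is Day 42, report Day 90 as well, so that late healing is visible.
- Report number and percent healed per graft with an exact interval, with the per-patient figure as a supplement, and state that 12.7 uses the per-graft figure on this set.
- Label mean and maximum healing time as healed grafts only, and give the median with failed grafts ranked longest.
- Show withdrawals unrelated to the graft separately, with results both counted as not healed and censored.
- A graft that healed before a later removal keeps its healing time; the removal is reported under safety.

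**(c) Sections 4 and 4.2.** List second grafts separately, and reconcile the two sections on whether a patient offered a second graft stays in the study. No clinical rule is proposed here.

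**Cost.** Changes to protocol and SAP wording, plus a few visits already in the calendar. The healing rate and survey scores may look slightly less favourable. Projection, diameter and sensitivity cannot be measured on a removed graft and should be reported as such.
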